8. SAFETY ANALYSES

The safety analyses will be based on the Safety population, unless otherwise specified.

8.1. Adverse Events Analyses

Adverse events analyses including the analysis of adverse events (AEs), Serious (SAEs), COVID-19 AEs and other significant AEs will be based on GSK Core Data Standards. The details of the planned displays are provided in Section [15.15](#): List of Data Displays.

8.1.1. Analyses for Injection Site Reaction Adverse Events from Study Drug Injection

Injection Site Reaction (ISR) adverse events of interest are those from study drug injections. For the summary of study drug ISR adverse events by visit and maximum severity (overall and by common ISRs): ISRs will be assigned based on onset date to the most recent planned IM injection visit prior or equal to the AE onset date.

Maximum grade at each visit will be derived as the maximum grade among ISRs assigned to the particular visit, with consideration for whether the summary applies to a particular preferred term (vs. across preferred terms), drug-related associated to CAB and/or RPV, or stratification by subgroup (such as needle length, refer to Section [5.4.2](#)).

Drug-related ISRs (based on investigator discretion) from study drug injections will be attributed to the causal agent (CAB vs. RPV) when this can be determined specifically based on the side of injection administration and the side of the reported ISR (as collected in the eCRF). If we are unable to determine the causal agent in those cases where both drugs are given on one side and the ISR is reported non-specifically, then the attribution to a specific causal agent will remain unknown.

Common study drug ISR adverse events are defined by MedDRA preferred terms including injection site pain, injection site induration, injection site nodules and preferred terms of any other ISR with $\geq 5\%$ participants in either treatment arm, coming from study drug injections. The same set of common terms will be applied to 'overall' (CAB and/or RPV), CAB alone, RPV alone.

Study drug ISRs will be attributed to the needle length (≤ 1.5 , > 1.5 to < 2 , ≥ 2 inches) specifically based on the side of injection administration and the side of the reported ISR (as collected in the eCRF). If we are unable to determine the needle length for events where both drugs are given on one side and their needle lengths are different, then the attribution to a needle length will remain unknown.

8.2. Adverse Events of Special Interest Analyses

Adverse events of special interest (AESI) are determined for CAB and/or RPV based on pre-clinical and clinical experience, along with information for the Integrase Inhibitor class of HIV medications and RPV safety profile. [Table 4](#) shows the currently identified AESI, drug(s) of Interest and the reasons for inclusion. Changes to the MedDRA dictionary may occur between the start of the study and the time of reporting, and/or

emerging data from on-going studies may highlight additional adverse events of special interest, therefore the list of AESIs may change at the time of reporting.

A summary by system organ class and preferred term will be provided for each of AESI. The characteristics of event occurrences will be summarized in main study for common AESI which have at least 20 participants in either treatment arm, and will be summarized in sub-study for common AESI which have at least five participants in either treatment arm. For Depression, anxiety and suicidal ideation/behaviour AESI, a summary by system organ class, maximum DAVIDS toxicity grade and prior history of suicidal ideation will be provided. The details of the planned grouping and planned displays are provided in Section 15.11 and Appendix 15: List of Data Displays.

Table 4 Adverse Events of Special Interest

| Adverse Events of Special Interest | Drug(s) of Interest | Reason for Inclusion |
|--|---------------------|--|
| Hepatic Safety Profile: Assessment of Risk of hepatotoxicity | CAB+RPV | Clinical, Class, Regulatory Interest, More prevalent in HIV population |
| Hypersensitivity Reactions (HSR) | CAB | Class, Regulatory Interest, Occurs in HIV population |
| Rash | RPV | Class, Regulatory Interest, Occurs in HIV population |
| Prolongation of the Corrected QT Interval of the ECG in Supratherapeutic Doses | RPV | Non-clinical, Clinical, Regulatory Interest |
| Suicidal Ideation/Behaviour | CAB+RPV | Clinical, Class, Regulatory Interest, More prevalent in HIV population |
| Depression | CAB+RPV | Clinical, Class, Regulatory Interest, More prevalent in HIV population |
| Bipolar Disorder | CAB+RPV | Clinical, Class, Regulatory Interest, More prevalent in HIV population |
| Psychosis | CAB+RPV | Clinical, Class, Regulatory Interest, More prevalent in HIV population |
| Mood Disorders | CAB+RPV | Clinical, Class, Regulatory Interest |
| Anxiety | CAB+RPV | Clinical, Class, Regulatory Interest |
| Sleep Disorders | CAB+RPV | Clinical, Class, Regulatory Interest, More prevalent in HIV population |

| Adverse Events of Special Interest | Drug(s) of Interest | Reason for Inclusion |
|--|---------------------|---|
| Injection Site Reactions (ISR) from Study Drug Injections [1] | CAB+RPV | Clinical |
| Seizures and Seizure-like Events | CAB | Clinical, Regulatory Interest |
| Weight Gain | CAB | Clinical, Class |
| Rhabdomyolysis | CAB | Clinical, Class |
| Pancreatitis | CAB | Clinical, Therapeutic Area, More prevalent in HIV population |
| Impact on Creatinine | CAB+RPV | Regulatory Interest, Therapeutic Area, More prevalent in HIV population |
| Safety in Pregnancy | CAB | Regulatory Interest, Class |
| Hyperglycaemia | CAB | Class, Regulatory Interest |
| NOTE: [1] A separate analysis will be performed for ISRs from study drug injections as described in Section 8.1.1. | | |

8.3. Clinical Laboratory Analyses

Laboratory evaluations including the analysis of results of Chemistry laboratory tests, Haematology laboratory tests, Urinalysis, and liver function tests will be based on GSK Core Data Standards. The details of the planned displays are in [Appendix 15: List of Data Displays](#).

8.4. Other Safety Analyses

The analyses of non-laboratory safety test results including ECGs and vital signs will be based on GSK Core Data Standards, unless otherwise specified. The details of the planned displays are presented in [Appendix 15: List of Data Displays](#).

ECG values of potential clinical importance are defined as a QTc of > 500 msec or increase from baseline in QTc ≥ 60 msec.

9. PHARMACOKINETIC ANALYSES

The GSK Division of Clinical Pharmacology Modelling and Simulation (CPMS) will be responsible for the PK analysis of CAB. The Division of Clinical Pharmacology and Pharmacometrics at Janssen Research and Development will be responsible for conduct or oversight of the PK analysis for RPV.

9.1. Endpoint / Variables

9.1.1. Drug Concentration Measures

Refer to [Appendix 5](#) Data Display Standards & Handling Conventions (Section 15.5.3 Reporting Standards for Pharmacokinetic)

9.2. Overview of Planned Analyses

[Table 5](#) provides an overview of the planned analyses with full details being presented in [Appendix 15](#): List of Data Displays. All PK displays will be based on the PK Population, unless otherwise specified.

Table 5 Overview of Planned Pharmacokinetic Analyses

| | Stats Analysis | | | Summary | | Individual | |
|--|----------------|---|---|---------------------|------------------------|------------------|---|
| | T | F | L | T | F | F | L |
| Pharmacokinetic [5] | | | | | | | |
| Plasma CAB concentration by visit | | | | Y ^{[1][2]} | Y ^{[1][3][4]} | Y ^[3] | Y |
| Plasma RPV concentration by visit | | | | Y ^{[1][2]} | Y ^{[1][3][4]} | Y ^[3] | Y |
| Steady state concentration | Y | | | | | | |
| Plasma CAB parameters by dosing interval | Y | Y | | Y | | | Y |
| Plasma RPV parameters by dosing interval | Y | Y | | Y | | | Y |

NOTES:

- T = Table, F = Figure, L = Listings, Y = Display generated.
- Stats Analysis = Represents TFL related to any formal statistical analyses (i.e. modelling) conducted.
- Summary = Represents TF related to any summaries (i.e. descriptive statistics) of the observed raw data.
- Individual = Represents FL related to any displays of individual participant observed raw data.
- Unless otherwise specified, all displays for evaluable concentrations except for individual displays will be presented by both overall and the rederived randomization strata.

1. For both 'all' concentration and the 'evaluable' concentration. The evaluable concentration is derived from samples collected within pre-specified Time window (Section 15.6.5)
2. For both 'untransformed' and 'log-transformed' statistics.
3. The plots will be produced for the untransformed scale (i.e., a linear plot) and the log transformed scale (i.e., log-linear plot), separately.
4. Separate plots will be produced for Mean (SD) and Median concentration.
5. Standard summary statistics for concentration data will be calculated (i.e., mean, standard deviation, coefficient of variation, median, minimum and maximum). For Logarithmically transformed data, the summary statistics (i.e. geometric mean, between subject coefficient of variation, 95% confidence interval for the geometric mean and standard deviation) will also be calculated.

9.3. Statistical Analyses / Methods

| |
|---|
| Planned PK statistical analysis |
| Steady State Concentration |
| Endpoints |
| 
 log_e-transformation of the Trough/Pre-dose evaluable plasma concentrations (CAB/RPV) on Week 16-48 (i.e. Weeks 16, 24, 32, 40 and 48) for participants receiving Q8W study treatment |
| Covariates |
| 
 Study Week |
| Data Handling |
| 
 All data remains as is (observed). |
| Model Specification |
| 
 A mixed effects ANOVA model will be fitted for each rederived randomization stratum [prior exposure to CAB+RPV (0 weeks, 1-24 weeks, >24 weeks)] with Study Week (continuous variable) as a fixed effect and subject as a random effect for each analysis separately. The Kenward & Roger (KR) degrees of freedom approach will be used. The coefficient for the slope of the week effect on the log_e-scale will be used to evaluate steady state for each drug (CAB/RPV). The 90% confidence intervals for the slope for each treatment will be calculated. If it does not appear that steady-state has been demonstrated, early weeks (e.g. Week 16, 24, etc...) results will be dropped and the analysis repeated. |
| Model Checking & Diagnostics |
| 
 The steady state will be claimed (the coefficient for the slope of the week effect on the (natural) log scale was close to 0 or the 90% CI for the slope estimate included zero. If steady-state is not demonstrated, concentrations from early weeks (e.g. Week 16, 20, 24, etc...) dropped in sequence and the analysis repeated until either steady state is shown or only two timepoints remain. |
| Model Results Presentation |
| 
 The coefficient for the slope of the week effect on the log_e-scale, its standard error and 90% interval will be presented for each rederived randomization stratum. |
| PK Parameters |
| Endpoints |
| 
 As data permit, Log_e-transformation of the PK parameters (C_{tau}, C_{max} and AUC(0-τ) for each sub-study dosing interval (refer to Section 15.6.5 for definition of the dosing interval) for participants enrolled in the sub-study |
| Model Specification |
| 
 Following Log_e-transformation, PK parameters will be separately analyzed by treatment arm and analyte using a mixed effects model with dosing interval (gluteal injection, first thigh injection and last thigh injection) as fixed effects and subject as random effects. In each model, only subjects with evaluable PK parameter estimates in both dosing intervals are included. For example, in the model for comparing C_{max} estimated from the first CAB thigh |

| |
|--|
| injection interval with Cmax estimated from the gluteal injection interval among Q8W subjects, only the Q8W subjects with evaluable Cmax estimates from both first CAB thigh injection interval and gluteal injection interval are included. |
| Model Checking & Diagnostics |
| 
Model assumptions will be applied, but appropriate adjustments may be made based on the data. |
| Model Results Presentation |
| 
The estimated difference and 90% CI obtained on the \log_e scale will be exponentiated to provide an estimate of geometric mean ratio and its associated 90% CI. The estimate of within-subject variability (%CVw) will also be provided. |

10. POPULATION PHARMACOKINETIC ANALYSES

The Population PK analyses will be described under a separate Population-PK Reporting and Analysis Plans for CAB LA and RPV LA

11. PHARMACOKINETIC / PHARMACODYNAMIC ANALYSES

The primary goal of this analysis is to characterize the pharmacokinetic / pharmacodynamic relationship of CAB/RPV administered in participants with HIV-1-infection who are virologically suppressed. The influence of subject demographics and baseline characteristics and additional subgroups/covariates in this population will be investigated.

11.1. Overview of Planned Analyses

Table 6 provides an overview of the planned analyses with full details being presented in Appendix 15: List of Data Displays. All PK displays will be based on the PK Population, unless otherwise specified.

Table 6 Overview of Planned Pharmacokinetic / Pharmacodynamic Analyses

| | Stats Analysis | | | Summary | | Individual | |
|---|----------------|---|---|---------|---|------------|---|
| | T | F | L | T | F | F | L |
| CAB/RPV Week 8 concentrations by snapshot 'HIV-1 RNA \geq 50 c/mL' (Yes vs. No) at Week 48 for participants without prior exposure to CAB+RPV | | | | Y | Y | | |
| Analysis of snapshot 'HIV-1 RNA \geq 50 c/mL' at Week 48 by Week 8 trough concentration, and subgroup [1] – univariable analysis /multivariable analysis for participants without prior exposure to CAB+RPV | Y | | | | | | |
| Individual CAB/RPV concentration-time profiles for participants with snapshot 'HIV-1 RNA \geq 50 c/mL' at Week 48 or 96 or 152 | | | | | Y | | |
| Maximum change from baseline in ALT/Total Bilirubin versus last trough CAB/RPV concentrations for Week 48 and Week 152 analyses[2] | | | | | Y | | |
| Change from baseline in pre-dose QTcF versus CAB/RPV concentrations at Week 48 or 152 | | | | | Y | | |
| Maximum toxicity grades of most frequently reported study drug ISR AEs [3] versus last trough CAB/RPV PK concentrations for Week 48 analysis[2] | | | | | Y | | |

NOTES:

- T = Table, F = Figure, L = Listings, Y = Display generated.
- Stats Analysis = Represents TFL related to any formal statistical analyses (i.e. modelling) conducted.
- Summary = Represents TF related to any summaries (i.e. descriptive statistics) of the observed raw data.
- Individual = Represents FL related to any displays of individual participant observed raw data.

1. Refer to Section [11.2](#).
2. Display by rederived randomization strata, i.e. prior exposure to CAB+RPV (0, 1-24, >24 weeks) derived based on eCRF.
3. Most frequently reported study drug ISR AEs are those top 5 in incidence in either treatment arm (i.e. Q8W or Q4W arm).

11.2. Statistical Analyses / Methods

| PK/PD Efficacy Analysis for Participants without Prior Exposure to CAB+RPV | |
|--|--|
| Endpoints | |
| 
 Snapshot 'HIV-1 RNA\geq50 c/mL' at Week 48 | |
| Covariates | |
| 
 Treatment, demographic and baseline characteristics except for country and Prior Exposure to CAB+RPV (0, \geq1 weeks), and additional subgroup/covariates for PK/PD efficacy analysis - see derivation details in Section 5.4.2. | |
| Data Handling | |
| 
 All data remains as is (observed). | |
| Model Specification | |
| 
 Logistic regression will be used to exam the correlation between the endpoint (Snapshot 'HIV-1 RNA\geq50 c/mL') at Week 48 and the covariates/subgroups. This logistic regression analysis will be performed for each covariate or subgroup, separately (univariable analysis), and will also be performed with one multivariable analysis using Backward stepwise selection approach to identify the covariates/subgroups potentially affecting virologic response. | |
| Model Checking & Diagnostics | |
| 
 For the multivariable analysis, a logistic regression model that best predicts the dependent variable (i.e. snapshot 'HIV-1 RNA\geq50 c/mL') from the independent variables (i.e. covariates/factors with P $<$0.15 from univariable analysis) will be determined using the backward stepwise selecting approach. Week 8 trough PK concentration will be logarithmically transformed with base of 2 (i.e. one-unit increase of the point estimate of log2 PK concentration is equivalent to 'doubling the concentration' in the original value). The analysis will start with all covariates in the model and remove a covariate with the largest p-value (i.e. the least statistically significant) each time and continue until the stopping rule is reached when all remaining covariates have p-value $<$15%. If problems with model convergence occur due to zero event counts or complete/quasi-complete separation, then alternative methods such as exact logistic regression may be used. | |
| Model Results Presentation | |
| 
 The odds ratio, 95% confidence interval, and p-value will be presented. | |

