| Demographic and Baseline Characteristic Subgroups | 
 • Age: 
 ○ < 35, 35 - < 50, ≥ 50 
For the statistical modelling, '< 35' and '35 - < 50' will be consolidated i.e. the following age group will be used:
 
 ○ < 50, ≥ 50 
For the summary of demographic characteristics, the following age groups will also be presented:
 
 ○ ≤ 18, 19 - 64, ≥ 65 (FDAAA requirement) ○ 18 - 64, 65 - 84, ≥ 85 (EMA requirement) • Race: 
 ○ White, Non-White ○ Black/African American, Non-Black/African American 
For the statistical modelling, only White vs Non-White is considered.
 • Sex at birth: 
 ○ Female ○ Male • Country (not used for statistical modelling) 
 ○ Argentina ○ Australia ○ Canada ○ France ○ Germany ○ Italy ○ Korea, Republic of ○ Mexico |

| Category | Covariates and / or Subgroups |
|----------|--|

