| | 
  Russian Federation  South Africa  Spain  Sweden  United States • Baseline CD4+ cell count (cells/mm³): 
  <350  350 - < 500  ≥ 500 • Baseline HIV-1 RNA (c/mL): 
  <50  ≥ 50 • Derived Baseline Centers for Disease Control and Prevention (CDC) category: 
  Stage I  Stage II  Stage III • Prior Exposure to CAB+RPV: 
  0 weeks  ≥ 1 weeks 
This subgroup will be used in efficacy analysis, in addition to the redrived randomization strata (prior exposure to CAB+RPV: 0, 1-24, and >24 weeks). It will also be used in health outcomes analysis. In other types of analysis, only the redrived randomization strata will be used.
 • Baseline BMI (kg/m²) 
  <30  ≥30 • Baseline Third Agent Class: 
  CAB+RPV (for subjects with prior exposure to CAB+RPV in ATLAS, i.e. subjects transitioning from ATLAS who received CAB+RPV in ATLAS before entering ATLAS-2M)  NNRTI INI  PI • Baseline Genotypic Subgroup Variables: 
The Baseline genotypic data became available for most of the subjects after the Week 48 analysis data cut, the following subgroups will be used in post-Week 48 analyses as appropriate. The baseline genotypic data for subjects transitioning from ATLAS comes from ATLAS PBMC samples collected at Baseline and the baseline genotypic data for new subjects comes from ATLAS-2M PBMC samples collected at Baseline. Different types of mutation are defined in Section 15.6.7.
 
  Baseline HIV-1 Subtype: 
 ▪ A, A1, AG Combined ▪ B |

| Category | Covariates and / or Subgroups |
|--|---|

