| | 
 ▪ C ▪ Other ○ Baseline L74I (Non-mixture) INSTI Mutation: 
 ▪ Present ▪ Not Present ○ Baseline Pre-specified INSTI Mutation (Excluding L74I Non-mixture): 
 ▪ Present ▪ Not Present ○ Baseline RPV RAM: 
 ▪ Present ▪ Not Present ○ Baseline NNRTI RAM (Excluding RPV RAM): 
 ▪ Present ▪ Not Present |
| EMA Subgroup Category 3: | |
| Additional subgroup/covariates for PK/PD efficacy analysis | 
PK/PD efficacy analysis will be performed for participants without prior exposure to CAB + RPV.
 
 ● Week 8 CAB/RPV Trough PK concentration (i.e. pre-dose PK concentration at nominal visit of Week 8) 
The above covariate will be dichotomized into two subgroup factors as follows:
 
 ○ \leq first Quartile vs $>$ first quartile, ○ \leq Median vs $>$ Median 
The concentration will also be treated as continuous variable in logistic regression modelling analysis (i.e. the concentration data will be \log_2 transformed in this analysis so that, for assessing the effect, one unit increase of the point estimate of \log_2 PK concentration is equivalent to 'doubling the concentration' in the original value).
 
 ● Length of First CAB/RPV Injection Needle (<2, ≥ 2 inches) |
| Additional subgroup/covariates for PK/PD safety analysis | 
Last CAB/RPV trough PK concentration
 
For the plot of Maximum Change from Baseline (CFB) in ALT/Total Bilirubin versus Last Trough CAB/RPV PK Concentrations, Last CAB/RPV Trough PK Concentration is the most recent trough PK concentration prior or equal to the date of the lab assessment with maximum CFB during the maintenance phase.
 
For the Plot of Maximum Toxicity Grades of Most Frequently Reported Study Drug ISR adverse events (AEs) versus Last Trough CAB/RPV PK Concentrations, Last CAB/RPV Trough PK Concentration is the most recent trough PK concentration prior or equal to the earliest onset date of the most frequently reported Study Drug ISR AE with maximum toxicity grade, during the maintenance phase. If a participant has no Study Drug ISR AE most commonly
 |

| Category | Covariates and / or Subgroups |
|--|--|
| | reported, then the last trough value during the maintenance phase will be used for the plot. |

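### The exploratory PK/PD logistic models cut baseline BMI, age and CD4+ into categories; if the effects are roughly log-linear this discards information that continuous terms would keep, about half of it for BMI

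*SAP*

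**What the plan says.** SAP Section 11.2 states its method thus: "Logistic regression will be used to exam the correlation between the endpoint", the endpoint being Snapshot HIV-1 RNA >=50 c/mL at Week 48. The covariates are treatment, "demographic and baseline characteristics except for country and Prior Exposure to CAB+RPV", and the additional PK/PD covariates, with derivations referred to Section 5.4.2. Each covariate is tested alone. Those with p <0.15 go into a multivariable model, which is reduced backwards until every remaining term has p <0.15.

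Section 5.4.2 fixes the coding:

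- **Age.** "For the statistical modelling, '< 35' and '35 - < 50' will be consolidated i.e. the following age group will be used": <50 and >=50 years.
- **BMI.** <30 and >=30 kg/m², with no continuous version.
- **CD4+ count.** <350, 350 to <500 and >=500 cells/mm³, with no continuous version.
- **Week 8 trough concentration.** Cut at the first quartile and at the median, but "The concentration will also be treated as continuous variable in logistic regression modelling analysis", after a log2 transformation.

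On the analysis set, Section 5.4.2 says: "PK/PD efficacy analysis will be performed for participants without prior exposure to CAB + RPV".

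The categorical coding is explicit for age. For BMI and CD4+ it follows because Section 11.2 points to Section 5.4.2 and no other derivation appears there.

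**The concern.** The purpose of Section 11.2 is to find covariates that may affect virologic response, so ability to detect them matters. Cutting a continuous covariate treats everyone on one side of the cut as alike. A real gradient may then miss the p <0.15 univariable screen and never reach the multivariable model.

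The SAP gives no reason for handling these three covariates differently from trough concentration. The EMA guideline cited in Section 5.4.2 is used to classify subgroup factors; nothing in that section ties it to the form of regression covariates. Section 11.2 also anticipates zero event counts and separation, and a cut that leaves a small group makes those more likely.

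**Working it through.** **Stated figure.** There is none to reproduce. The SAP gives no power, event rate, number without prior exposure, BMI distribution or effect size for this analysis.

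**Assumed inputs.** About 500-650 participants without prior exposure (49-64% of the 1020 randomised), failure rate 1.5-3%, share with BMI >=30 of 15-25%, odds ratio (OR) 1.5-2.0 per SD of BMI, log-linear effect. Two-sided alpha is 0.05, and also 0.15 because that is the SAP's own threshold.

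**Step 1: information kept by the BMI cut.** For a normal covariate cut at c with share s above it, relative efficiency is φ(c)² / [s(1 − s)].

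- s = 0.15: c = 1.036, φ = 0.233; 0.0544 / 0.1275 = 0.43
- s = 0.20: c = 0.842, φ = 0.280; 0.0784 / 0.1600 = 0.49
- s = 0.25: c = 0.674, φ = 0.318; 0.1010 / 0.1875 = 0.54

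**Step 2: approximate check on one case.** With 600 × 0.02 = 12 events and OR 1.5, the noncentrality is √12 × ln 1.5 = 3.464 × 0.405 = 1.405. Power at 0.05 is about Φ(1.405 − 1.96) = 29%. With the cut and s = 0.20, the noncentrality falls to 1.405 × √0.49 = 0.983, and power to about 17% counting both tails.

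**Step 3: simulation.** Likelihood-ratio tests, 2000 runs per scenario, 20% at or above 30, power in per cent. Losses are taken before rounding. Events are 600 × 0.015 = 9, 600 × 0.02 = 12 and 650 × 0.03 = 19.5.

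| Events | OR per SD | Continuous, 0.05 | Cut, 0.05 | Loss | Continuous, 0.15 | Cut, 0.15 | Loss |
|---|---|---|---|---|---|---|---|
| 9 | 1.5 | 22.6 | 16.0 | 6.6 | 41.1 | 32.2 | 8.8 |
| 9 | 2.0 | 51.9 | 34.8 | 17.1 | 70.6 | 55.6 | 15.0 |
| 12 | 1.5 | 27.9 | 18.3 | 9.6 | 47.8 | 34.9 | 12.9 |
| 12 | 2.0 | 64.4 | 43.6 | 20.8 | 79.6 | 64.8 | 14.8 |
| 19.5 | 1.5 | 42.4 | 25.2 | 17.2 | 62.6 | 43.4 | 19.2 |
| 19.5 | 2.0 | 83.2 | 62.3 | 20.9 | 93.0 | 78.0 | 15.0 |

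The third row (27.9 against 18.3) agrees with Step 2 (29 against 17).

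**Step 4: sensitivity.**

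- With 9-12 events and 15-25% above the cut, the loss at 0.05 is 6.6 to 21.7 points.
- At a 3% rate with only 15% above the cut, it reaches 24.1 points (OR 1.75) and 25.9 points (OR 2.0).
- At 0.15, the loss for OR 1.5-2.0 stays between 7.7 and 20.2 points.
- With OR 1.25 and 5-12 events it is close to zero, and slightly negative in a few cells.
- A separate simulation with log-normal BMI (median 26, 20% at >=30, n = 500-650, rate 1.5-3%, OR 1.5-2.0, 1500 runs) gave losses of 8-19 points at 0.05 and 7-17 at 0.15.
- If risk truly steps up near 30, the cut loses nothing.

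No corresponding calculation was made for age or for three-band CD4+; there the loss depends on where the cuts fall.

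**The case against.** The strongest objection is that the size rests wholly on assumptions. That stands: the SAP supplies none of the inputs, so any number of points is conditional. Even a very low event count is an inference from the separation clause, not a stated rate. Power is also modest under either coding when events are few (23% against 16% at 9 events and OR 1.5), and the concentration-response objective is listed as exploratory in Section 2.2. These points limit the weight of the matter but do not reverse its direction.

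Timing stands too. The univariable and multivariable tables are Week 48 deliverables only (Section 15.15.5.8), the Week 152 PK/PD list holds figures only (Section 15.15.6.8), and Section 5.4.2 speaks of the Week 48 data cut as past. A change now is more than an edit of wording.

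A reader might go further in two ways that the SAP does not support.

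- **That the cut also lets through more false positives at the 15% screen.** With 20% above the cut and a 1.5% rate, exact enumeration under no effect gives 22.7% (n = 500) and 20.4% (n = 650) for a likelihood-ratio test, but 8.4% and 8.7% for Wald and 9.3% and 10.2% for Fisher's exact test. Section 11.2 does not name the test, and it offers exact logistic regression as a possible remedy when zero counts or separation cause convergence problems.
- **That a screened-out BMI term leaves the trough estimate confounded by body size.** If body size acts on failure by lowering trough, then trough is a mediator, and omitting BMI does not confound it. Confounding needs a separate path from BMI to failure, which nothing in the SAP establishes.

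**Conclusion.** The coding choice is confirmed, and continuous terms would be the better specification. Under a roughly log-linear effect, the BMI cut keeps about 43-54% of the information. With 500-650 participants, a 1.5-3% failure rate and OR 1.5-2.0 per SD, that costs roughly 7-22 points of power at 0.05 (up to 26 in the corner with a 3% rate and 15% above the cut) and 7-20 points at 0.15. Over wider assumptions the range is about 0 to 26, with no loss under a step near 30. It would be wrong to read any of these as a cost that the SAP itself demonstrates, or to carry them over to age and CD4+.

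This is a cheap improvement to an exploratory analysis. No primary or key secondary conclusion depends on it.

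**What to change.** In the univariable and multivariable models of Section 11.2, enter baseline BMI (per 5 kg/m²), age (per 10 years) and CD4+ count (per 100 cells/mm³) as continuous terms, in line with log2 trough concentration. Check linearity on the logit scale. Keep the Section 5.4.2 categories for the subgroup tables and forest plots.

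This needs no new data and no extra parameters: BMI and age use one degree of freedom either way, and CD4+ goes from two to one. The price is the assumption of linearity, which can be checked only weakly with few events. Because the Week 48 data cut has passed, present any re-run as a supplementary post-hoc analysis beside the planned one.
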